### **3.3 Study Treatments and Assessments**

The maximum study duration from screening to end of the evaluation phase is 29 ( $\pm$  2) days.

There will be two treatment groups in this study.

- ISV-305 group
- Vehicle group

ISV-305 is a topical ophthalmic formulation of 0.1% dexamethasone in DuraSite 2. The vehicle utilized in this study is the same formulation as ISV-305 (i.e., DuraSite 2) without dexamethasone.

All subjects eligible for study participation will enter from Screening/Randomization Phase (Visit 1) to the Dosing Phase. During the Dosing Phase (Day -1 to Day 14), subjects will be dosed BID for 16 days: the day before cataract surgery, the day of cataract surgery, and for 14 days after cataract surgery. Subjects will then be followed for approximately 2 weeks during the Evaluation Phase (Day 15 to Day 29). There will be 7 study visits for full study participation: 1 visit during the Screening/Randomization Phase, 3 visits (Day 0, Day 1 and Day 8) during the Dosing Phase, and 3 visits (Day 15, Day 18, and Day 29) during the Evaluation Phase.

## 4.0 STUDY ENDPOINTS

### 4.1 Primary Efficacy Endpoint

The primary efficacy endpoint is the proportion of subjects with an ACC grade of 0 at Day 15.

Anterior Chamber Cells	
Grade*	Cell Count
0	0
1	1-5
1	6-10
2	11-20
3	21-50
4	> 50

\*Grade 1 includes cell count 1-5 and cell count 6-10.

### 4.2 Key Secondary Endpoints

The secondary efficacy endpoints are the proportion of subjects who achieve a pain score of 0 on the visual analog scale (VAS) (0-100 mm scale) for each post-surgical assessment at Days 1, 8, 15, 18, and 29.

### 4.3 Safety Endpoints

The safety endpoints of this study are:

- Incidence of ocular adverse events and serious adverse events
- Incidence of non-ocular adverse events and serious adverse events
- Measurement/evaluation and change from baseline in the study eye at each scheduled visit for the following ocular-specific parameters:
  - BCVA
  - IOP
  - Slit-lamp biomicroscopy
  - Ophthalmoscopy findings
  - Photophobia

## 5.0 ANALYSIS POPULATIONS

All efficacy endpoints will be analyzed using the modified intent-to-treat (mITT) population. The Per-Protocol (PP) population will be used for the analysis of the primary and secondary endpoints to examine the robustness of the primary analyses.

Safety and tolerability will be analyzed using the safety population.

### 5.1 Intention-To-Treat Population (ITT)

The ITT population includes all randomized subjects, regardless of whether post-baseline measures are collected or IP is received. Subjects in the ITT population will be analyzed in the treatment group to which they were assigned by the randomization scheme, regardless of which

IP, if any, they receive. This population will be used in the disposition and protocol deviation summaries.

## **5.2 Modified Intent-To-Treat Population (mITT)**

The mITT population includes randomized subjects that undergo cataract surgery, receive at least one dose of IP, and have at least one post-surgery efficacy assessment. Subjects who receive rescue medications will be included in the mITT but will be treated as failures. This population will be used in all efficacy analyses. Subjects in the mITT population will be analyzed in the treatment group to which they were assigned by the randomization scheme, regardless of which IP if any, they receive.

## **5.3 Per-Protocol Population (PP)**

The per protocol (PP) population includes all subjects in the mITT population excluding those subjects who receive rescue medications or have major protocol violations that may compromise their efficacy data.

## **5.4 Safety Population (Safety)**

The Safety population includes all randomized subjects who receive at least 1 dose of IP. Subjects in the safety population will be analyzed according to the IP they actually received. This population will be used in all safety analyses.

## **6.0 STATISTICAL CONSIDERATIONS AND ANALYSIS**

### **6.1 Derived Variables**

The below text provides the list of derived variables for demographic and baseline characteristics, various duration derivations, drug compliance, baseline derivations and other important derivations applicable for this study.

#### **Study Days**

Study Day 0 represents the day of surgery. Subjects will instill doses daily, starting on Day –1 and continuing through Day 14.

Study days for the remaining visits will be based on the date of surgery and calculated as:

- (visit/assessment date – date of surgery).

#### **Baseline**

Unless stated otherwise the baseline value for a variable will be the value taken at Visit 1/Screening Visit.

#### **Definitions Relative to Demographic and Other Baseline Characteristics - Age**

Age at informed consent will be calculated as:

Age (years) = (date of informed consent - date of birth + 1) / 365.25

### 6.1.1 Definitions Relative to Efficacy Parameters

#### **Proportion of Subjects with ACC Grade 0 at a Given Time Point**

Proportion = Number of responders at Day X / Total number of subjects in the mITT population

Notes:

1. Responders are those subjects who had ACC grade of 0 either at Day X or the last assessment prior to Day X visit (in case the Day X was not completed).
2. Those subjects who received a rescue medication between and including Day 0 and X will be considered as treatment failure or non-responder, despite a subject with zero cell count either at Day X or the last assessment prior to Day X visit (in case the Day X was not completed).

#### **Proportion of Subjects with VAS Pain Score 0 at Each Time Point**

Proportion = Number of subjects with zero score for VAS Pain / Total number of subjects in the mITT population

The VAS is a measure of overall self-rated health status. It ranges from 0 to 100 using a mark on a 100 mm line, with 0 score indicative of no pain and 100 indicative of maximum pain.

### 6.1.2 Definitions Relative to Safety and Tolerability Parameters

In order to assess the safety and tolerability of ISV-305 compared to Vehicle group in subjects with cataract surgery, adverse events will be observed throughout the entire study.

#### **Adverse Event (AE)**

An AE is defined as any untoward medical occurrence associated with the use of an IP in humans, whether or not considered related to the IP. An AE can therefore be any unfavorable and unintended sign, symptom or disease temporally associated with the use of an IP, without any judgment about causality. An AE can arise from any use of the IP (e.g., off-label use, use in combination with another drug) and from any route of administration, formulation or dose, including overdose.

Medical conditions or diseases present before a subject starts study treatment are only considered AEs if they worsen after the subject signs informed consent.

#### **Serious Adverse Event (SAE)**

A Serious Adverse Event (SAE) is defined as an event that, in the view of either the investigator or sponsor, results in any of the following outcomes:

- death
- a life-threatening AE or sight-threatening AE, where ophthalmics are involved
- inpatient hospitalization or prolongation of existing hospitalization
- a persistent or significant incapacity or substantial disruption of the ability to conduct normal life functions

- a congenital anomaly/birth defect
- an important medical event that may not result in death, be life-threatening/sight-threatening, or require hospitalization may be considered serious when, based upon appropriate medical judgment, they may jeopardize the subject and may require medical or surgical intervention to prevent one of the outcomes listed above. Examples of such events are intensive treatment in emergency room or at home for allergic bronchospasm; blood dyscrasias or convulsions that do not result in hospitalization; or development of drug dependency or drug abuse.

The criterion of inpatient hospitalization is met if the subject is admitted to the hospital as the result of an AE, even if the subject is released on the same day. An emergency room visit does not qualify as “inpatient hospitalization” unless the subject is admitted to the hospital during the visit; however, the reason for the emergency room visit may qualify as an SAE based on another SAE criteria (e.g., life threatening or medically significant event).

### **Pre-existing Conditions**

Pre-existing condition is defined as a disorder/disease present before the AE-reporting period starts (i.e., prior to the subject signing the ICF) and noted on the Medical History eCRF. A preexisting condition will not be reported as an AE unless the condition worsens or episodes increase in frequency during the AE-reporting period.

### **Duration of AEs**

The duration of an AE will be calculated as the resolution date minus the date of onset plus 1. In the case of an AE still continuing at the end of the study, the duration will be considered as unknown.

## **6.2 Handling of Missing Data and/or Invalid Data and Outliers**

### **6.2.1 Missing Data Analysis Methods for Efficacy Data**

The Last Observation Carried Forward (LOCF) method will be used to impute missing values for the primary and all secondary endpoints. In LOCF imputation, missing Day X values will be imputed using the last non-missing observation prior to Day X.

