3.2 Exclusion Criteria

The following are exclusion criteria for prospective study subjects to be confirmed at Visit 1 (Day -14 – Day -2) prior to randomization. The sponsor will not grant any protocol eligibility waivers.

- a. Have a history of Fuchs' dystrophy in the study eye
- b. Have a history of diabetic retinopathy (with visual impairment) and/or previous vitrectomy in the study eye within the last 2 years
- c. Have any sign of iritis or scleritis in the study eye

- d. Have a history of glaucoma surgery in the study eye within the last 2 years
- e. Have an existing diagnosis of severe dry eye in the study eye
- f. Have known hypersensitivity or poor tolerance to any component of the IP or any of the procedural medications such as anesthetic and/or fluorescein drops, dilating drops, etc.
- g. Have an acute ocular infection (bacterial, viral or fungal) or active ocular inflammation in the study eye
- h. Have any extraocular/intraocular inflammation in the study eye noted prior to surgery (blepharitis is allowed if scurf only without any concurrent conjunctivitis or lid erythema/edema) or ongoing, unresolved uveitis
- i. Use of the following disallowed medications within a specified amount of time before surgery:
 - topical, inhaled, or oral corticosteroids within 15 days
 - depot-corticosteroids within 45 days (triamcinolone within 90 days)
 - topical, systemic, or inhaled nonsteroidal anti-inflammatory drugs (NSAIDs) within 1 week (with the exception of low-dose aspirin)
 - ocular or systemic antihistamines, or mast cell stabilizers within 1 week
 - other analgesics and use of acetaminophen (Tylenol[®]) within 48 hours
 - any medication that the investigator feels may interfere with the study parameters
- j. Have any active or chronic/recurrent ocular or systemic disease that is uncontrolled and likely to affect wound healing (e.g., diabetes mellitus, systemic connective tissue disease, severe atopic disease)
- k. Have known blood dyscrasia or bone marrow suppression
- l. Have any active corneal pathology noted in the study eye
- m. Have any intraocular inflammation (cells or flare in anterior chamber) or ocular pain (greater than 0) on the pain scale in either eye
- n. Have had radial keratotomy, corneal transplant, or LASIK in the study eye within the last 2 years
- o. Be currently pregnant, nursing, or planning a pregnancy, or be a woman that has a positive pregnancy test
- p. Are currently suffering from alcohol and/or drug abuse

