6.2 Examination Procedures

The following ophthalmic examinations will be conducted in the surgery eye (study eye) at intervals specified in Table 1, The Schedule of Assessments. The fellow eye (non-study eye) may be examined at the investigators' discretion.

- **Best Corrected Visual Acuity (BCVA):** BCVA will be measured at every visit except Visit 2 (Surgery; Day 0). The Early Treatment Diabetic Retinopathy (ETDRS) log of the minimum angle of resolution (logMAR) will be used to measure BCVA.
- **Intraocular Pressure (IOP):** IOP will be measured at every visit except Visit 2 (Surgery; Day 0) in mmHg using an applanation tonometer.
- **Ophthalmoscopy:** Ophthalmoscopy will be performed at Visit 1 (Day -14 to Day -2) and Visit 5 (Day 15) by a board-certified ophthalmologist.
- **Biomicroscopy:** Slit lamp biomicroscopy, including the evaluation of ACC and anterior chamber flare (ACF), chemosis, bulbar conjunctival injection, ciliary injection, corneal edema, and keratic precipitates will be conducted by a board-certified ophthalmologist at every visit except Visit 2 (Surgery; Day 0).
- **Visual Analog Scale (VAS):** Eye pain/discomfort and photophobia will be evaluated at every visit except Visit 2 (Surgery; Day 0) using a Visual Analog Scale (VAS), scoring from 0 to 100 using a mark on a 100 mm line (0 = absent; 100 = maximum).
- **Pain assessment via diary (Pain Diary):** Surgery eye pain will be evaluated prior to each IP dose using a pain scale included in the pain and dosing diary that subjects complete at home.

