### **7.4.2 Analysis of Primary Efficacy Endpoint**

The primary efficacy endpoint is the proportion of subjects with an ACC grade of 0 at Day 15.

The difference between treatment groups will be tested using a two-sided Z-Test with continuity correction and pooled variance using the mITT population. A subject with an ACC grade of 0 at the Day 15 visit or the last assessment prior to the Day 15 visit (in the event that Day 15 was not completed) will be considered a responder to therapy. If a subject has an ACC score of >0 at Day 15 or the last assessment prior to the Day 15 visit (in the event that Day 15 was not completed), that subject will be considered a failure (or non-responder) in the primary efficacy endpoint analysis. Additionally, any subject receiving a rescue medication between Day 0 and the Day 15 visit (inclusive) will be considered a treatment failure.

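### Last-observation-carried-forward is not limited to post-surgery values, so as written a missing Day 1 VAS pain score takes the pre-surgery screening score, very likely 0, and counts as pain-free

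*SAP*

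**What the plan says.** SAP 6.2.1 applies last observation carried forward (LOCF) to the primary and all secondary endpoints: "missing Day X values will be imputed using the last non-missing observation prior to Day X". For anterior chamber cells (ACC) the same idea appears twice. SAP 6.1.1, note 1: "Responders are those subjects who had ACC grade of 0 either at Day X or the last assessment prior to Day X visit". SAP 7.4.2: "A subject with an ACC grade of 0 at the Day 15 visit or the last assessment prior to the Day 15 visit", when Day 15 was not completed. None of these places says that the carried value must come from after surgery.

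The pain endpoint in SAP 4.2 is a VAS score of 0 "for each post-surgical assessment at Days 1, 8, 15, 18, and 29". SAP 6.1.1 computes it as "Number of subjects with zero score for VAS Pain / Total number of subjects in the mITT population", so a subject with a missing score stays in the denominator. SAP 7.4.3 repeats LOCF for this endpoint and adds multiple imputation to assess its effect.

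Protocol 6.1 (Table 1) and 6.2 schedule the VAS at Visit 1 and at every later visit except the day of surgery. Protocol 3.2, criterion m, excludes subjects who "Have any intraocular inflammation (cells or flare in anterior chamber) or ocular pain (greater than 0) on the pain scale in either eye".

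**The concern.** LOCF after an intervention assumes that the earlier value says something about the later one. A screening score from an eye that has not been operated on says nothing about pain the day after surgery, yet it is the only scheduled VAS before Day 1. Entry criteria push that score to 0, which is exactly the response value. The imputation would then turn missing data into treatment successes in either arm.

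Three things are at stake:
- The reported Day 1 pain-free rates are too high whenever a missing subject in fact had pain.
- If missingness differs between arms, the Day 1 comparison shifts toward the arm with more missing data, and that p-value enters the Hochberg procedure.
- One programmer may follow the text literally while another assumes the usual post-baseline convention, and they would report different Day 1 results.

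**Working it through.** **Tracing the rule**

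1. Subject: had surgery, took at least one dose, received no rescue medication, and has some post-surgery efficacy assessment but no Day 1 VAS. SAP 5.2 keeps this subject in the mITT, since any one post-surgery efficacy assessment suffices.
2. Value carried forward: the last non-missing VAS before Day 1. The only scheduled one is Visit 1. An unscheduled VAS after surgery would replace it.
3. Its level: criterion m requires no ocular pain at Visit 1. That the scale meant there is the VAS is an inference. Protocol 6.2 also uses the term for the home diary ("Surgery eye pain will be evaluated prior to each IP dose using a pain scale included in the pain and dosing diary"), but the VAS is the only pain measure scheduled at Visit 1.
4. Result: score 0, so the subject is pain-free on Day 1.

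**Reach elsewhere.** Day 8 VAS is affected only if Day 1 is also missing. The primary is affected only if no post-surgery ACC exists by Day 15. Criterion m also bars cells at screening, so such a subject would be a responder. Each one moves the rate by at most 1/160 = 0.63 points (ISV-305) or 1/80 = 1.25 points (vehicle).

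**Size on Day 1.** The documents give no pain-free or missing-data rates and no figure to reproduce, so all rates below are assumptions. The group sizes, 160 and 80, are in Protocol 2.0. Let p be the true pain-free rate and m the share missing, unrelated to outcome within arm.

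- Rate under the written rule: p(1−m) + m
- Overstatement: p(1−m) + m − p = m(1−p)
- At p = 0.30: 0.02 × 0.70 = 1.4 points; 0.05 × 0.70 = 3.5 points; 0.10 × 0.70 = 7.0 points

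**Effect on the test.** This is an exact binomial enumeration of the SAP's two-sided pooled Z-test with continuity correction 0.5(1/160 + 1/80). There is no true difference and p = 0.30. Hochberg over five time points compares the largest p-value with 0.05 and the smallest with 0.05/5 = 0.01, so both levels are shown.

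| Missing, ISV-305 / vehicle | Rejects at 0.05 (single test) | Rejects at 0.01 |
|---|---|---|
| 0% / 0% | 3.5% | 0.6% |
| 5% / 5% | 3.5% | 0.6% |
| 5% / 2% | 4.4% | 0.8% |
| 6% / 2% | 5.1% | 1.0% |
| 10% / 2% | 10.3% | 2.8% |

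In the last row the analysed rates are 0.30 × 0.90 + 0.10 = 37.0% and 0.30 × 0.98 + 0.02 = 31.4%, a spurious difference of 5.6 points.

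**Effect on power** (single test at 0.05). For 45% vs 30% with 5% missing per arm, power is 51.4% under the written rule and 53.8% using observed subjects only (152/76). For 35% vs 20%, the direction depends on which arm has more missing data: 43.0% with 2% / 5% missing, 59.4% with 2% / 2% and 70.4% with 5% / 2%.

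**The case against.** The strongest reply is that nobody intends this. No section says that screening values are carried forward. The endpoint is defined for post-surgical assessments, mITT entry requires one, and LOCF commonly means post-baseline values only. This has weight as to intent, and a reader should not infer that the sponsor chose to count screening scores as outcomes. But those sections fix the time points and the population, not which values may be carried. If the post-surgery reading is accepted, a missing Day 1 VAS has no scheduled value to carry, and the SAP gives no rule for that subject in the tested analysis. A sentence is needed on either reading.

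The second reply is that few subjects can be affected: those who miss the VAS at the first postoperative visit, have no unscheduled VAS before it, and receive no rescue (rescued subjects are failures under SAP 5.2). Nothing suggests that such subjects are common or unevenly spread. This stands and limits the severity.

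The third reply is that the multiple imputation in SAP 7.4.3 would help to reveal a distortion. It would, but it does not change the LOCF result that is tested.

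A reader might also infer from the 10.3% figure that the trial's type I error is inflated. The documents do not support that. The figure is for one unadjusted test with a missingness gap that nothing in them suggests, it falls to 2.8% at the 0.01 step, and the test is reached only after the primary succeeds (SAP 7.4.1.2).

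**Conclusion.** The point holds as a minor defect. Followed as written, the LOCF rule can supply a pre-surgery value for a post-surgery outcome, mainly for Day 1 VAS pain. That this value is 0 is very likely but rests on reading the scale in criterion m as the VAS.

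Under the assumed rates, the Day 1 pain-free rate is overstated by m(1−p), or 3.5 points at 5% missing and a 30% true rate. The comparison is hardly affected when missingness is equal, and it is materially distorted only under a marked imbalance.

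A reader might go further and conclude that the primary analysis is compromised. It is not: a subject would need to lack every post-surgery ACC through Day 15 and still be in the mITT, which should be rare. Nor do the documents show that multiple imputation must replace LOCF in the tested analysis. That choice is debatable, and it would raise the further question of how to combine continuity-corrected Z-tests across imputations.

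**What to change.** In SAP 6.2.1, 6.1.1 note 1 and 7.4.2, state that only post-surgery values of the same variable may be carried forward, including those from unscheduled and early-exit examinations, and that screening values never are.

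Before unmasking, name one rule for a subject with no such value by Day X, for example counting the subject as a non-responder. This is a new missing-data convention and should be stated as such, not treated as an extension of the rescue-failure rule. Keep the multiple imputation already planned in SAP 7.4.3 as the sensitivity check for VAS.

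The cost is one or two sentences and one programming condition, and reported rates fall slightly. Non-responder counting has its own bias under unequal missingness. With 10% vs 2% missing and no true difference, single-test rejection at 0.05 (written rule against non-responder) is 10.3% against 5.2% at a 30% pain-free rate, 7.5% for both at 50%, and 4.3% against 14.3% at 80%. It is therefore worse than the written rule when the pain-free rate is above 50%, which is why the sensitivity check should stay.

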### **6.2.2 Handling of Missing or Incomplete Dates**

#### **Definition of Treatment-emergent AEs and Handling of Missing or Incomplete Dates**

A Treatment-Emergent AE (TEAE) is defined as an AE occurring or worsening on or after the first IP dose. Events with an onset date at or after the subject has signed the ICF and prior to the first IP dose will be classified as pre-treatment AEs.

In the event of an incomplete onset date, the event will be considered to be treatment-emergent unless the partial onset date information or complete or partial end date confirms onset or end prior to the first IP dose date (worst case approach).

For AEs listings, dates will be presented as they have been recorded (missing and partial dates will not be replaced).

### **Imputation Rules for Missing or Partial AE Start Dates**

If only Day of AE start date is missing:

If the AE start year and month are the same as that for the first dose of IP date, then:

- If the full (or partial) AE end date is NOT before the first dose of IP date or AE end date is missing, then impute the AE start day as the day of first IP date.
- Otherwise, impute the AE start day as 1.

If Day and Month of AE start date are missing:

If AE start year = first dose of IP year, then:

- If the full (or partial) AE end date is NOT before the first dose of IP date or AE end date is missing, then impute the AE start Month and Day as the Month and Day of first dose of IP date.
- Otherwise, impute the AE start MONTH as January and the DAY as 1.

